**PROTOCOL TITLE**

The Coma Recovery Scale-Revised for Accelerated Standardized Assessment (CRSR-FAST): an abbreviated assessment of conscious awareness for patients with disorders of consciousness (DOC)

**FUNDING**

National Institute on Disability, Independent Living, and Rehabilitation Research, U.S. Department of Health and Human Services

**VERSION DATE**

02/08/2023

**SPECIFIC AIMS**

Concisely state the objectives of the study and the hypothesis being tested.

**Specific Aims:**

Determine the reliability, validity, sensitivity/specificity and administration time of the CCSR-FAST in the acute care setting.

**Hypotheses:**

Hypothesis 1: Concurrent validity between CCSR-FAST and CRS-R total scores will be adequate.

Hypothesis 2: Inter-rater reliability of CCSR-FAST-derived diagnostic ratings (conscious v. unconscious) will be adequate.

Hypothesis 3: Test-retest reliability of CCSR-FAST-derived diagnostic ratings (conscious v. unconscious) will be adequate.

Hypothesis 4: Internal consistency between the CCSR-FAST total score and the four subscale scores will be adequate.

Hypothesis 5: The sensitivity of the CCSR-FAST in detecting features of MCS (using the CRS-R as a reference standard) will be adequate.

**Hypothesis 6:** The average administration time for the CRSR-FAST when administered in the acute care setting will be  $\leq$  10 minutes.

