### Neurobehavioral Assessment

Patients will be assessed using the CRS-R and the CCSR-FAST. The CRS-R is a standardized neurobehavioral rating scale that consists of 23 items organized into six subscales that address arousal, auditory, visual, motor, oromotor/verbal, and communication systems. Each subscale is organized hierarchically, with lower items representing reflexive behaviors and higher items indicative of cognitively-mediated behaviors. Reliability and validity have been demonstrated in multiple studies. The CCSR-FAST consists of 10 items organized into 4 subscales that address arousal, visual, motor and verbal/oromotor systems. Each subscale is organized hierarchically, with lower items representing reflexive behaviors and higher items indicative of cognitively-mediated behaviors.

An independent member of the study team (i.e., not an examiner) will screen patients at MGH for eligibility through a medical chart review. When a patient meeting the inclusion/exclusion criteria is identified, the study PI and study coordinator will be notified. The study coordinator will work with the patient's clinical team to determine an appropriate time to approach the family for consent. Consent may be conducted remotely or in-person at MGH. Once consent is obtained, the coordinator will work with the family and clinical team to determine an appropriate time to conduct the CCSR-FAST and CRS-R assessment(s). The study will conclude when a sample size of approximately 75 subjects is reached.

The study will be conducted across approximately 4 sessions completed over one or two consecutive days and will be carried out by three independent examiners (A, B, and C). For example:

Examiner A will administer the standard CRS-R and examiners B and C will administer the CRSR-FAST. This will enable calculation of concurrent validity (CRS-R v. CRSR-FAST) as well as inter-rater reliability of the CRSR-FAST (CRSR-FAST Rater A v. CRSR-FAST Rater B). Examiner C will administer the CRSR-FAST twice over a short interval to enable calculation of intra-rater reliability (CRSR-FAST Rater C at Time 1 v. CRSR-FAST Rater C at Time 2).

Examiners may include [name], [name], a dedicated TBI Model Systems research assistant, postdoctoral fellow, and a surgical intensive care unit Fellow.

The test administration order will be pseudo-randomized to prevent order effects and each test administration will be timed.

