## **Statistical Analysis Plan**

Examiners documented the start and end time of each assessment to determine the feasibility of the CRSR-FAST (goal: mean  $\leq$ 10 minutes). We tested concurrent validity by comparing CRS-R and CRS-FAST diagnostic ratings (conscious [MCS or eMCS] vs. unconscious [coma or VS/UWS]), using the simple Kappa coefficient and CRSR-FAST test-retest and inter-rater reliability using Mak's  $\rho$  (Statistical Analysis System [SAS v9.4]). We established an a priori threshold of  $\geq 0.60$  to indicate substantial validity and reliability

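### Hypothesis 1 is about total scores, but the SAP's only concurrent-validity analysis is a kappa on the conscious/unconscious rating, so Hypothesis 1 as worded is not tested

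*Combined protocol and SAP*

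**What the plan says.** The Hypotheses section uses two different variables. Hypothesis 1 is on the totals: "Concurrent validity between CCSR-FAST and CRS-R total scores will be adequate". Hypothesis 2 is on the diagnosis: "Inter-rater reliability of CCSR-FAST-derived diagnostic ratings (conscious v. unconscious) will be adequate". Hypothesis 3, on test-retest reliability, uses the same diagnostic rating as Hypothesis 2.

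The Statistical Analysis Plan tests concurrent validity by "comparing CRS-R and CRS-FAST diagnostic ratings (conscious [MCS or eMCS] vs. unconscious [coma or VS/UWS]), using the simple Kappa coefficient". It assigns Mak's rho to the two reliability questions and sets one a priori mark of 0.60 or more "to indicate substantial validity and reliability".

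The Neurobehavioral Assessment section describes the CRS-R as "23 items organized into six subscales that address arousal, auditory, visual, motor, oromotor/verbal, and communication systems" and the new scale as "10 items organized into 4 subscales that address arousal, visual, motor and verbal/oromotor systems". On the comparison it says only "This will enable calculation of concurrent validity (CRS-R v. CRSR-FAST", without stating whether totals or ratings are meant. In its example, examiner B gives the CRSR-FAST once, and "Examiner C will administer the CRSR-FAST twice over a short interval".

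The scale appears as CCSR-FAST, CRSR-FAST and CRS-FAST. These appear to be one instrument, and the point does not depend on the spelling.

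**The concern.** The first listed hypothesis names one variable and the analysis uses another. If the SAP is followed as written, concurrent validity will be declared met or not met at 0.60 while the stated question, how closely the two totals track each other, has no analysis.

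A reader who takes the kappa as the answer to Hypothesis 1 could be misled either way. A satisfactory kappa does not guarantee a strong total-score correlation, and a kappa just under 0.60 does not rule one out. An undisclosed change of variable also weakens the claim that the 0.60 mark was fixed in advance for the hypothesis it is used to judge.

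**Working it through.** **Step 1: compare the texts.**

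| Question | Variable in the hypothesis | Variable and statistic in the SAP |
|---|---|---|
| H1, concurrent validity | Total scores | Binary rating, simple kappa |
| H2, inter-rater reliability | Binary rating | Mak's rho |
| H3, test-retest reliability | Binary rating | Mak's rho |

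The hypotheses distinguish total from rating, so the word 'total' in Hypothesis 1 is hard to read as loose drafting. The design text names the two scales but not the variable, so it does not close the gap. The finding rests on this step alone.

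**Step 2: ask how far the two quantities could differ.** The documents give 75 subjects and the 0.60 mark. They give no expected kappa, correlation or proportion conscious, so there is no plan figure to reproduce. Everything below is illustration under assumed inputs.

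*Model 1: each rating is a cut on its own total.* Totals are bivariate normal with correlation r, and both scales call the same proportion p conscious. With p11 the probability that both say conscious:

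- observed agreement po = 1 - 2p + 2·p11
- chance agreement pe = p² + (1-p)²
- kappa = (po - pe)/(1 - pe)

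Example: r = 0.80 and p = 0.5 give p11 = 0.3976, po = 0.7952, pe = 0.50, and kappa = 0.2952/0.50 = 0.59.

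| r | p = 0.2 or 0.8 | p = 0.3 or 0.7 | p = 0.5 |
|---|---|---|---|
| 0.60 | 0.37 | 0.39 | 0.41 |
| 0.80 | 0.56 | 0.58 | 0.59 |
| 0.90 | 0.69 | 0.70 | 0.71 |

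A kappa of 0.60 needs r = 0.837, 0.821 and 0.809 in the three columns. If the scales call different proportions conscious, 40% and 60%, then r = 0.90 gives po = 0.777, pe = 2 × 0.4 × 0.6 = 0.48, and kappa = 0.297/0.52 = 0.57. A strong correlation can therefore miss the mark.

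Simulated samples of 75 with equal marginals and 30 to 70% conscious reach an observed kappa of 0.60 in about 3% of cases when true r = 0.60, and in about 41 to 45% when true r = 0.80. So under this model the kappa does carry information about the totals.

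*Model 2: the rating is not a cut on the total.* Let s be the share of each total's variance lying between its rating groups, and w the within-group correlation of the totals. With equal marginals kappa equals the correlation of the two ratings. If the within-group residuals are independent of both ratings, then at kappa = 0.60:

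r = 0.60s + w(1 - s)

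| w | s = 0.3 | s = 0.5 | s = 0.7 |
|---|---|---|---|
| 0.3 | 0.39 | 0.45 | 0.51 |
| 0.5 | 0.53 | 0.55 | 0.57 |
| 0.7 | 0.67 | 0.65 | 0.63 |
| 0.9 | 0.81 | 0.75 | 0.69 |

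For example, w = 0.3 and s = 0.3 give 0.18 + 0.21 = 0.39. Here a kappa exactly at the mark is compatible with a modest correlation.

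**Step 3: precision of the missing analysis.** For an observed Spearman correlation of 0.60 at n = 75, the approximate 95% CI is tanh(atanh(0.60) ± 1.96 × sqrt((1 + 0.60²/2)/72)). The standard error is sqrt(1.18/72) = 0.128, and the interval is 0.415 to 0.737.

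**The case against.** The strongest reply is that agreement on consciousness is what the tool is for. The Background section stresses sensitivity to signs of consciousness, so a kappa on the rating may be the more useful form of validity. That stands, and it is why the kappa should be kept. It does not turn the kappa into an analysis of totals.

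A reader might go further than the documents allow and infer that the kappa says nothing about Hypothesis 1, neither supporting nor refuting it. That is too strong. Both quantities come from the same examinations, and both scales are ordered from reflexive to cognitively mediated behaviour. Under Model 1 a kappa of 0.60 is rarely observed unless the totals correlate well. The kappa is indirect evidence.

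Three further objections have weight:

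- The weak correlations in Model 2 need a low within-group correlation, which nothing in the documents supports or excludes. The models show that the size of the gap is unknown, not that it is large.
- Differing item content (23 items in six subscales against 10 in four) affects ratings as well as totals, so it does not by itself separate the two questions. The contrast in wording between Hypothesis 1 and Hypotheses 2 and 3 does that.
- The SAP is only a few sentences long and may be condensed. It also names no analysis for Hypothesis 4 (internal consistency) or Hypothesis 5 (sensitivity), which is a separate gap. But its statement on concurrent validity is complete: it gives variable, statistic and threshold, and the variable is not the one in Hypothesis 1.

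**Conclusion.** The inconsistency is real and should be corrected before results are reported against Hypothesis 1. As written, the SAP does not test that hypothesis: it applies a stated analysis to a different variable, with no disclosure of a change. This conclusion rests on the text and needs no modelling assumption.

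The practical size cannot be fixed from the documents. Across the assumed models, a kappa of 0.60 corresponds to a total-score correlation from 0.39 (Model 2, w = 0.3, s = 0.3) to 0.84 (Model 1, 20% or 80% conscious). The documents do not support saying that the kappa is the wrong analysis, that it is uninformative about the totals, or that the totals agree poorly.

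**What to change.** Do one of two things.

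**A. Keep Hypothesis 1 and add its analysis.** Possible SAP wording: *Hypothesis 1 is assessed by the Spearman correlation between CRS-R and CRSR-FAST total scores, with 95% CI, using one named CRSR-FAST administration per patient; the kappa for diagnostic rating uses the same pair.* Spearman is one reasonable choice among several. The protocol's example yields up to three CRSR-FAST scores per patient, so the administration must be named; examiner B's single one is an option. Report the kappa as agreement on diagnostic rating. The 0.60 mark is worded generally but stated alongside kappa and Mak's rho, so say whether it was meant to apply to a correlation. If it was not, report the estimate and CI without pass or fail.

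**B. Amend Hypothesis 1.** If the binary rating is the intended target, say so in Hypothesis 1 and state when and why it changed.

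In either case date the change. The SAP is in the past tense, so label as post hoc any analysis or mark added after data were seen.

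**Cost.** A adds one routine analysis and B is a disclosed wording change. Both scales are already given to the same patients, so no new data are needed.

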## **BACKGROUND AND SIGNIFICANCE**

Provide a brief paragraph summarizing prior experience important for understanding the proposed study and procedures.

The CRS-R^1 is a standardized and validated bedside assessment of conscious awareness. It is used routinely for diagnosis and prognosis of patients with disorders of consciousness (DOC) as well as in research settings. One limitation of the CRS-R is the lengthy administration time required to obtain a total score. Administration time can vary from approximately 15-30 minutes, depending on the patient's level of responsiveness. For this reason, the CRS-R is rarely administered in the acute hospital setting. Less time-consuming scales and metrics are used to assess conscious awareness in the acute hospital/ICU setting, but they lack specificity and sensitivity and have not been validated, increasing the potential for misdiagnosis. In conjunction with the developers of the Neuroscore (an unpublished, abbreviated version of the CRS-R^3), we have developed the CRSR-FAST and aim to test its validity, inter- and intra- rater reliability. We anticipate that, compared with the CRS-R, the CRSR-FAST will be less time-consuming to administer and score, but will maintain a high level of sensitivity to detecting signs of consciousness in severely brain injured patients.

## **RESEARCH DESIGN AND METHODS**

Briefly describe study design and anticipated enrollment, i.e., number of subjects to be enrolled by researchers study-wide and by Partners researchers. Provide a brief summary of the eligibility criteria (for example, age range, gender, medical condition). Include any local site restrictions, for example, "Enrollment at Partners will be limited to adults although the sponsor's protocol is open to both children and adults."

Study design: prospective, cross-sectional study

Participants: 75 subjects

### **Inclusion Criteria:**

- Age 18 or older
- Fluent in English
- Surrogate available to provide informed consent
- History of severe acquired brain injury
- Sustained a TBI (defined by damage to brain tissue caused by an external mechanical force),
- Be within 3 weeks of injury
- Have a total GCS score  $<9$  within the first 48 hours of injury,

- Be unable to follow simple commands consistently at the time of enrollment

### **Exclusion Criteria:**

- History of developmental, neurologic, or major psychiatric disorder resulting in ongoing functional disability up to the time of the current injury
- Physician orders for comfort measures only

The following clinical factors will necessitate deferral of enrollment until the condition or symptom has resolved:

- Evidence of a reversible medical condition or symptom that is judged to be a safety concern or threat to the validity of the assessment, as deemed by treating physician

Briefly describe study procedures. Include any local site restrictions, for example, “Subjects enrolled at Partners will not participate in the pharmacokinetic portion of the study.” Describe study endpoints.

### Neurobehavioral Assessment

Patients will be assessed using the CRS-R and the CCSR-FAST. The CRS-R is a standardized neurobehavioral rating scale that consists of 23 items organized into six subscales that address arousal, auditory, visual, motor, oromotor/verbal, and communication systems. Each subscale is organized hierarchically, with lower items representing reflexive behaviors and higher items indicative of cognitively-mediated behaviors. Reliability and validity have been demonstrated in multiple studies. The CCSR-FAST consists of 10 items organized into 4 subscales that address arousal, visual, motor and verbal/oromotor systems. Each subscale is organized hierarchically, with lower items representing reflexive behaviors and higher items indicative of cognitively-mediated behaviors.

An independent member of the study team (i.e., not an examiner) will screen patients at MGH for eligibility through a medical chart review. When a patient meeting the inclusion/exclusion criteria is identified, the study PI and study coordinator will be notified. The study coordinator will work with the patient's clinical team to determine an appropriate time to approach the family for consent. Consent may be conducted remotely or in-person at MGH. Once consent is obtained, the coordinator will work with the family and clinical team to determine an appropriate time to conduct the CCSR-FAST and CRS-R assessment(s). The study will conclude when a sample size of approximately 75 subjects is reached.

The study will be conducted across approximately 4 sessions completed over one or two consecutive days and will be carried out by three independent examiners (A, B, and C). For example:

Examiner A will administer the standard CRS-R and examiners B and C will administer the CRSR-FAST. This will enable calculation of concurrent validity (CRS-R v. CRSR-FAST) as well as inter-rater reliability of the CRSR-FAST (CRSR-FAST Rater A v. CRSR-FAST Rater B). Examiner C will administer the CRSR-FAST twice over a short interval to enable calculation of intra-rater reliability (CRSR-FAST Rater C at Time 1 v. CRSR-FAST Rater C at Time 2).

Examiners may include [name], [name], a dedicated TBI Model Systems research assistant, postdoctoral fellow, and a surgical intensive care unit Fellow.

The test administration order will be pseudo-randomized to prevent order effects and each test administration will be timed.

We will record concomitant medications, dosages and administration times.

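### Validity is judged on one pooled kappa of at least 0.60, which can be met with many CRS-R-conscious patients missed; the SAP reports neither sensitivity nor which CRS-R subscales the misses came from

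*Combined protocol and SAP*

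**What the plan says.** Under Neurobehavioral Assessment the protocol describes the short scale: "The CCSR-FAST consists of 10 items organized into 4 subscales that address arousal, visual, motor and verbal/oromotor systems". The reference CRS-R has "23 items organized into six subscales that address arousal, auditory, visual, motor, oromotor/verbal, and communication systems". So auditory and communication have no subscale of their own on the short form. (The documents spell the short scale's name in more than one way; I read all spellings as one instrument.) The same section orders the subscales of both scales "with lower items representing reflexive behaviors and higher items indicative of cognitively-mediated behaviors".

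The Specific Aims name sensitivity and specificity, and Hypothesis 5 reads: "The sensitivity of the CCSR-FAST in detecting features of MCS (using the CRS-R as a reference standard) will be adequate". It gives no number for adequate. Background and Significance also expects the short scale to stay highly sensitive.

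The Statistical Analysis Plan tests concurrent validity by "comparing CRS-R and CRS-FAST diagnostic ratings (conscious [MCS or eMCS] vs. unconscious [coma or VS/UWS]), using the simple Kappa coefficient", and a value of at least 0.60 counts as substantial. It also plans test-retest and inter-rater reliability by Mak's rho, and mean administration time. It contains no sensitivity or specificity analysis, nothing on the direction of disagreement, and no breakdown of discordant patients by CRS-R subscale.

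Two other places bear on the point. One inclusion criterion is "Be unable to follow simple commands consistently at the time of enrollment", which leaves inconsistent command-followers eligible. Foreseeable Risks and Discomforts says that both exams may use a noxious stimulus to test motor responses when the patient does not follow commands.

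**The concern.** The index test covers fewer named systems than its reference. Because the upper items of every CRS-R subscale mark cognitively mediated behaviour, a conscious rating on the CRS-R could plausibly rest on auditory or communication items alone. If the short scale does not pick up such a patient elsewhere, the error goes one way: conscious on the reference, unconscious on the short scale.

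Kappa does not distinguish that error from its opposite. It is a single index of agreement, and it can pass a fixed mark with all the disagreement on one side. The reliability analyses would not expose the problem either, since two raters, or one rater twice, can agree perfectly in missing the same patient.

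The protocol motivates the scale by misdiagnosis in acute care and hopes to give ICU clinicians a tool for detecting awareness. For that use the missed conscious patient is the error that matters most, and the SAP as written would not display it.

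**Working it through.** **The plan's own figure.** The sample size of 75 cannot be reproduced: the documents give no alpha, power, expected kappa, prevalence or precision target. It is taken as given and is not in dispute.

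**Inputs.** N = 75 (Research Design and Methods); simple kappa with a mark of 0.60 (SAP). Assumed, because the documents are silent: the share conscious by CRS-R, varied from 30% to 80%, and the false-positive rate, first none and then about 10%.

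**Formula.** Let P be the number conscious by CRS-R and m the number of these rated unconscious on the short scale. With no false positives:

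- observed agreement: po = (75 − m)/75
- chance agreement: pe = [P(P − m) + (75 − P)(75 − P + m)]/75²
- kappa = (po − pe)/(1 − pe)

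**Worked case, 60% conscious.** P = 45, m = 15. po = 60/75 = 0.80. pe = (45 × 30 + 30 × 45)/5625 = 2700/5625 = 0.48. kappa = 0.32/0.52 = 0.615. A third of the conscious patients are missed and the mark is met.

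**Most misses that still meet 0.60**

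| Assumed conscious | No false positives: missed | Sensitivity | Kappa | About 10% false positives: missed | Sensitivity |
|---|---|---|---|---|---|
| 30% | 10 of 22 | 0.545 | 0.629 | 7 of 22 | 0.682 |
| 40% | 13 of 30 | 0.567 | 0.611 | 9 of 30 | 0.700 |
| 50% | 15 of 38 | 0.605 | 0.602 | 11 of 38 | 0.711 |
| 60% | 15 of 45 | 0.667 | 0.615 | 12 of 45 | 0.733 |
| 70% | 15 of 52 | 0.712 | 0.602 | 12 of 52 | 0.769 |
| 80% | 12 of 60 | 0.800 | 0.615 | 9 of 60 | 0.850 |

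With no false positives the tolerated miss rate runs from 10/22 = 45% down to 12/60 = 20%. With about 10% false positives it runs from 7/22 = 32% to 9/60 = 15%.

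**Smaller misses.** At 50% conscious with no false positives, missing 4 of 38 gives kappa 0.893 and missing 8 of 38 gives 0.787. Both are well above the mark.

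**What sensitivity would look like at N = 75 (exact 95% intervals)**

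- 20/22 = 0.909 (0.708 to 0.989)
- 34/38 = 0.895 (0.752 to 0.971)
- 47/52 = 0.904 (0.790 to 0.968)

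For a very small subgroup, 5 of 5 detected has an exact lower limit of 0.025^(1/5) = 0.48, and 9 of 9 has 0.025^(1/9) = 0.66.

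**The case against.** A missing subscale is not a missing behaviour. The documents do not list the ten items of the short scale, and they do not give the item rule for MCS or eMCS on either scale. The wording under Foreseeable Risks and Discomforts suggests that command-following is tried within the short exam, so much of the auditory content may sit under motor. Speech might be scored under verbal/oromotor. Inconsistent command-followers are therefore not clearly an at-risk group, since responses to command are the very content that may be covered. All of this stands. A reader might infer that the short scale is bound by its structure to miss patients whose only sign is auditory or communicative; the documents do not show that.

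Nor do the kappa figures measure a content gap. They describe any one-directional miss, whatever its cause. The share of CRS-R diagnoses resting on auditory or communication items alone is unknown and may be near zero. That also stands. The figures show what the 0.60 mark tolerates, not what will happen.

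A table by subscale would not cleanly separate content from noise. The two scales are given by different examiners, in sessions that may span two days, and an isolated sign may simply fluctuate. The group would often be too small to support a claim of its own. This is why the table should be descriptive, with no pass rule attached to the subgroup.

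Finally, the study does name sensitivity as an aim. That is true, but it strengthens the point: the aim was not carried into the SAP.

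**Conclusion.** The concern holds in a limited form. The subscale mismatch is on the face of the protocol. The only validity criterion in the SAP is a pooled kappa of at least 0.60. Hypothesis 5's sensitivity has neither a threshold nor a planned analysis.

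If 30% to 80% of 75 patients are conscious by CRS-R and there are no false positives, the criterion can be met with about 45% to 20% of conscious patients missed. With about 10% false positives the range is about 32% to 15%. Prevalence and false-positive rate are assumptions.

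Whether any misses would arise from the absent auditory and communication subscales cannot be settled from the documents. That uncertainty is a reason to tabulate, not a finding against the scale. This is an inexpensive improvement to reporting rather than a flaw in the design.

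**What to change.** Amend the SAP in three respects.

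1. Beside kappa, report sensitivity and specificity of the short scale against the CRS-R diagnosis (conscious versus unconscious), each with an exact 95% interval and the full two-by-two counts.
2. State the item rule that makes a CRS-R rating conscious. Then list every CRS-R-conscious patient by the subscale or subscales that carried the conscious-level item, and by whether the short scale detected them. Cover all six subscales, and show as its own row the patients whose only such items are auditory, communication or both. Label the table descriptive.
3. Say that the scale will not be called valid for detecting consciousness on kappa alone if sensitivity is low.

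The SAP is written in the past tense, so analyses added now should be marked as added.

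The cost is a few lines of text and one table. The full CRS-R is already administered, so its subscale scores should be available and no further patients or assessments are needed. The auditory/communication-only row may hold very few patients with a wide interval, low detection there could reflect fluctuation as well as content, and the headline claim may become narrower.

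### Does the mislabelled rater pair, or the unstated choice between Examiner C's two ratings, undermine the inter-rater analysis of the CRSR-FAST?

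*Combined protocol and SAP*

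**What the plan says.** The Neurobehavioral Assessment section of the protocol says the study "will be carried out by three independent examiners (A, B, and C"), in about four sessions over one or two consecutive days. It then gives a layout, introduced as an example: "Examiner A will administer the standard CRS-R and examiners B and C will administer the CRSR-FAST". From this layout it derives concurrent validity and "inter-rater reliability of the CRSR-FAST (CRSR-FAST Rater A v. CRSR-FAST Rater B"). The following sentence has Examiner C repeat the CRSR-FAST after a short interval to obtain "intra-rater reliability (CRSR-FAST Rater C at Time 1 v. CRSR-FAST Rater C at Time 2"). The section adds: "The test administration order will be pseudo-randomized to prevent order effects".

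Hypothesis 2 reads "Inter-rater reliability of CCSR-FAST-derived diagnostic ratings (conscious v. unconscious) will be adequate" and names no raters. The Statistical Analysis Plan covers "CRSR-FAST test-retest and inter-rater reliability using Mak's" ρ, with a threshold of at least 0.60, and also names no pair and no time point.

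**The concern.** Two things look wrong.

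- **The label.** Read literally, the inter-rater pair needs a CRSR-FAST rating from Examiner A, and the example gives A none. The rater letters seem to follow the examiner letters, because the next sentence uses Rater C for Examiner C. Taken at face value, Hypothesis 2 would have no data.
- **The pairing.** Once the label is read as B against C, two coefficients qualify: B with C's first rating and B with C's second. The SAP says of its cut-off, "We established an a priori threshold of" 0.60 or more. A cut-off fixed in advance loses some of its force if the coefficient it applies to is not fixed as well. An analyst who saw both values could report the one that passes.

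**Working it through.** **Step 1: can the label be resolved from the text?** Count the administrations per patient in the example layout:

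| Examiner | Scale | Administrations |
|---|---|---|
| A | CRS-R | 1 |
| B | CRSR-FAST | 1 |
| C | CRSR-FAST | 2 |

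The total is 1 + 1 + 2 = 4, which agrees with the roughly four sessions stated and leaves none for a CRSR-FAST by A. The CRSR-FAST ratings are B, C1 and C2, which form three pairs: C1–C2 (intra-rater), B–C1 and B–C2 (both inter-rater). The only reading that fits the layout is B against C, and the data for it are collected. Because the layout is only an example, roles may differ between patients. The conclusion holds in either case, since the data are still two different examiners' CRSR-FAST ratings of the same patient.

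**Step 2: how far apart could the two candidate coefficients be?** The documents give no expected coefficient and no expected proportion conscious, so these are assumed:

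- n = 75 (protocol);
- 50% to 80% of ratings conscious;
- C's test-retest ρ 0.70 to 0.90;
- equal true agreement of B with C1 and with C2.

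The statistic is Mak's ρ = 1 − (mean within-patient discordance) / (mean between-patient discordance). Binary ratings were simulated from a dichotomised trivariate normal, 40,000 trials per setting.

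| True B–C ρ | Result |
|---|---|
| 0.60 to 0.70 | The two estimates lie on opposite sides of 0.60 in 9% to 32% of trials; SD of their difference 0.05 to 0.12 |
| 0.80 | Opposite sides in 1% to 5% |
| 0.55 | One fixed pair reaches 0.60 in 31% to 34%; the better of two in 39% to 48% |

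**Step 3: compare with ordinary sampling error.** Take a true ρ of 0.60 and treat the between-patient term as fixed.

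- 50% conscious: between-patient discordance 2 × 0.5 × 0.5 = 0.50; within-patient discordance 0.40 × 0.50 = 0.20. The standard error of ρ is √(0.20 × 0.80 / 75) / 0.50 = 0.046 / 0.50 ≈ 0.09.
- 80% conscious: between 2 × 0.8 × 0.2 = 0.32; within 0.40 × 0.32 = 0.128. The standard error is √(0.128 × 0.872 / 75) / 0.32 = 0.0386 / 0.32 ≈ 0.12.

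The difference between the two pairings (SD 0.05 to 0.12) is therefore no larger than the uncertainty in either coefficient alone (about 0.09 to 0.12).

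**The case for a change.** The best case for a change is that it would be cheap: a corrected label and one SAP sentence naming the C rating. Near the threshold the choice is not trivial. At a true ρ of 0.55, taking the better of two adds roughly 7 to 14 percentage points to the chance of passing. The documents give no expected coefficient, so they cannot rule that region out. The SAP is written in the past tense, so a reader cannot tell from it which pair was used. Nor does the pseudo-randomised order make C's ratings interchangeable: C's second rating always follows C's own first examination of the patient, and no masking to the first score is described.

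These facts stand, but they do not amount to a defect in the analysis. The harm depends on choosing after seeing both results, and nothing in the documents points to that. The 0.60 value is a descriptive benchmark for a point estimate, with no type I error rate attached. At a true ρ of 0.55, a single fixed pair already clears it about a third of the time, and naming the pair would leave that unchanged. The possible carry-over at C's second rating is a reason an analyst may prefer the first; it does not invalidate either coefficient. The simulation assumes equal agreement for both pairings, so it does not measure any such carry-over.

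**Conclusion.** No change to the plan is needed. The label is a clerical slip that alters no data, sample size, statistic or threshold, and Hypothesis 2 remains estimable. The open choice of C's rating is missing detail that an analyst fills sensibly by using one rating per examiner and saying which. Writing the choice down would record a decision without improving the estimate.

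The effect is confined to a true coefficient near 0.60: the two pairings disagree about the threshold in 9% to 32% of trials at a true ρ of 0.60 to 0.70, and in 1% to 5% at 0.80. These figures rest on the assumed proportion conscious, the assumed test-retest ρ and equal agreement of B with both C ratings, none of which the documents supply. When reading the results, check which pair the inter-rater coefficient refers to.
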